APPENDIX L: CASE REPORT FORMS112
APPENDIX M: INVESTIGATIONAL PLAN REVISIONS.....113

LIST OF TABLES

Table 1. Follow-up Windows	26
Table 2. Data Collection Summary.....	27
Table 3. Unavoidable Events	38
Table 4. Heart Mate II Study Rates	44
Table 5. Study Oversight Contact Information.....	60
Table 6. Investigator Reporting Responsibility	68
Table 7. Sponsor Reporting Responsibility	70

TABLE OF FIGURES

Figure 1. Study Design Flowchart	17
Figure 2 Annual Survival versus Hospitalization versus NYHA	58

Trial Contact Information

Sponsor, Manufacturer & Distributor	Sunshine Heart, Inc. [name] Tele: [name] [contact] www.sunshineheart.com
-------------------------------------	---

Clinical/Technical Support [contact]-SHCPULSE)

INTRODUCTION

PURPOSE

Sunshine Heart is sponsoring a prospective, multi-center, randomized trial to assess the safety and efficacy of the C-Pulse® System (“C-Pulse”).

The purpose of the study is to determine whether the use of the C-Pulse as a treatment for patients in moderate to severe heart failure (HF) has demonstrated safety and efficacy, such that the C-Pulse System merits Food and Drug Administration (FDA) approval to market the device in the United States.

STUDY SIZE AND DURATION

This clinical study is anticipated to commence October 2012. The enrollment and 12 month follow-up duration of the study is expected to be 3.5 years. The primary study population will include 388 subjects enrolled and randomized in up to 40 centers in the United States (US) and potentially additional sites in Canada. The treatment group will include 194 subjects randomized to and implanted with C-Pulse® System and the control group will include 194 subjects randomized to and followed according to the same follow-up schedule as the treated subjects. All patients must be consented prior to performing any study related procedures. A patient is considered enrolled upon signing the informed consent. To minimize the burden to the patient, data collected as standard of care and not for the specific reason for study eligibility may be used for baseline data points as outlined in the informed consent. These tests will suffice for the baseline dataset if collected within the specified baseline data collection timeframe prior to implant. The subjects will be assigned a screening number upon signing the consent.

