The study is a prospective, randomized, multi-center trial designed to demonstrate the safety and efficacy of the C-Pulse[®] System in relieving heart failure symptoms in patients with ACC/AHA Stage C, NYHA Class III to ambulatory Class IV heart failure. Reduction in heart failure symptoms will be demonstrated by increased freedom from heart failure related hospitalization or death in subjects implanted and treated with the C-Pulse System as compared to a concurrent, randomized control group receiving standard optimal medical therapy (OMT).

Patients will be enrolled into the trial upon providing informed consent. Procedures related directly to the study must not be performed prior to informed consent. Following confirmation of subject eligibility, subjects will be randomized to one of two treatment arms, Treatment or Control, in a 1:1 allocation utilizing a random permuted block design stratified by study center. The Treatment group subjects will receive the C-Pulse[®] System with immediate therapy following implant and OMT while the Control group will continue on OMT. The subjects will not be allowed to cross-over from the assigned group (i.e. a control will not be allowed to receive a C-Pulse). If a treatment subject is explanted, it will be reported in the study analysis per the statistical methods section.

This study will include up to 40 centers in the US and potentially some Canadian centers. The study population will include 388 patients. All subjects who meet eligibility requirements and sign study consent will then be randomized following the baseline testing completion. The follow-up period will be for a minimum of 12 months to assess the safety and efficacy. To facilitate the analysis of the therapeutic effect, it is desired that the system be used all the time. The subject must limit disconnection to a minimal amount of time allowed for personal convenience such as hygiene. The Driver logs subject usage automatically and stores this usage into the system files.

Subjects will be followed for up to five years.

If a subject undergoes anesthesia for the purpose of C-Pulse implantation but does not receive a C-Pulse System, the subject will be followed for 30 days for safety or until they are discharged, whichever occurs first.

[figure not shown]

Figure 1. Study Design Flowchart

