There is no published study using the same endpoint in a similar heart failure treatment population. The MEDAMACS study has an enrollment population similar to the target population for the C-Pulse System Pivotal Trial and has an endpoint close to the C-Pulse System primary endpoint except that all-cause mortality is included. The study reports a 6-month survival free from LVAD implant, heart transplant or inotrope use of 64%. As this likely represents a higher event probability than the C-Pulse System primary endpoint, a higher freedom from event at 6 months was calculated assuming half the mortality events were not due to worsening heart failure. As the 6 month freedom from all-cause mortality estimate was 84%, an estimate for freedom from worsening heart failure event of 72% is chosen for the Control group estimate. The current proposed study was therefore powered to detect a 30% reduction in the probability of worsening heart failure event (an assumed hazard ratio of 0.70). The C-Pulse System Feasibility Study has an estimated freedom from worsening heart failure event of 95.0% at 6 months and 72.4% at 12 months, however, as this is based on 20 subjects the confidence limits of the estimate are wide and it is therefore not a desirable estimate on which to entirely base the sample size assumptions.

The study is powered to detect a statistically significant difference in freedom from worsening heart failure events favoring Treatment over Control. Worsening heart failure events represent an objective measure of worsening heart failure and an observed reduction would represent a clinically significant and meaningful improvement in heart failure subjects' health. The planned secondary analyses will provide supporting evidence of superiority in the improvement of QOL and other clinical parameters demonstrating the effectiveness of C-Pulse therapy in relieving heart failure related symptoms and associated morbidity.

Primary Safety Endpoint

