1. If the test statistic for the primary endpoint crosses the futility threshold, the DSMB may recommend that enrollment be discontinued for futility.
2. If the test statistic for the primary endpoint crosses the efficacy threshold the DSMB may make one of the following recommendations:
 - A. recommend that the trial be stopped for efficacy
 - B. recommend that the control arm be dropped as the enrollment of the treatment arm continues in order to achieve a minimum of 12 months of follow-up on a defined number of implanted subjects
 - C. recommend that the trial continues as planned to obtain a better precision on the treatment effect.
3. If neither the futility nor the efficacy boundaries are crossed, the DSMB may recommend that trial enrollment and follow-up continue as planned.

Secondary Efficacy Endpoints

The following secondary endpoints will be analyzed according to the objectives and hypothesis tests given below. Testing of the hypothesis driven secondary efficacy objectives will be conducted only in the event the primary efficacy objective and primary safety objectives are met, thereby preserving an overall Type I error rate of 5%. The secondary efficacy endpoints and associated analyses are described below:

1. Improvement in 6 Minute Hall Walk at 12 months

The improvement in 6 Minute Hall Walk will be computed as the difference between the baseline and follow-up value at 12 months. Subjects not evaluated at 12 months due to prior VAD implant, heart transplant or death will have the worst possible outcome imputed for improvement. Subjects unable to perform the 6MHW will have a value of 0 for the 12 month result. Improvement at 12 months will be compared between treatment groups under the following hypotheses.

Hypotheses

$$H_0: DT = D_c$$

$$H_A: DT \neq D_c,$$

where DT represents the distribution of improvement in 6MHW for the Treatment and D_c the distribution of improvement in 6MHW for Control. Details of the analysis methods can be found in the Statistical Analysis Plan.

2. Improvement in 6 Minute Hall Walk at 18 months

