The poolability of the primary efficacy endpoint across clinical sites will be assessed using a covariate adjusted proportional hazards regression model including an interaction term for clinical site and treatment group. In the event statistical evidence of a difference in treatment effect by site is found, an analysis utilizing a random effects model with a random effect for site will be conducted.

Type I Error Control for Secondary Objectives

The secondary efficacy objectives will be tested in a hierarchical fashion in the order listed only in the event the primary efficacy objective is met, thereby preserving an overall Type I error rate of 5%.

Handling of Missing Data

For the primary efficacy analysis, subjects lost to follow-up or explanted will be censored at the date of the last assessment.

Additional analyses of the follow-up assessments of KCCQ, six minute walk and LVEF will be conducted to assess the impact of missing data at month 12. The Wilcoxon Sign-Rank test with the worst rank imputed for data missing due to death, LVAD transplant, heart transplant or explant (in order of time to outcome) will be used to assess treatment differences in the continuous parameters while including subjects who withdrew from randomized treatment prior to the 12 month assessment. Multiple imputation analyses will be conducted to assess the robustness of the study results against data missing due to losses to follow-up and study non-compliance or un-interpretable test results.

Impact of Covariates on the Potential Treatment Differences

Additional exploratory statistical analyses of the primary and secondary study results will be conducted to assess for impact of selected baseline and follow-up parameters on the observed treatment differences. This will involve the stratification of results by categorical parameters and covariate adjusted regression analyses for the assessment of interaction with randomization assignment. Of particular interest will be an assessment for any treatment differences in the efficacy or safety parameters by gender. Other baseline covariates of interest will include classification based on race/ethnicity, age at implant, INTERMACS profile, NYHA, etiology (ischemic/non-ischemic), CRT/ICD therapy, angina, arrhythmia, hyperlipidemia and diabetes and the continuous covariates of baseline six-minute walk, KCCQ and MLWHF.

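### The month-12 missing-data check names a paired test for a between-arm comparison, and two sections state the gate to secondary testing differently

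*Combined protocol and SAP*

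**What the plan says.** **Test.** The Handling of Missing Data section announces further analyses of KCCQ, six-minute walk and LVEF that "will be conducted to assess the impact of missing data at month 12". The method is "The Wilcoxon Sign-Rank test with the worst rank imputed for data missing due to death, LVAD transplant, heart transplant or explant", with the imputed ranks ordered by time to the outcome, and it "will be used to assess treatment differences in the continuous parameters". The section then adds: "Multiple imputation analyses will be conducted to assess the robustness of the study results". That part is aimed at loss to follow-up, non-compliance and uninterpretable tests.

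The Design section allocates subjects "in a 1:1 allocation utilizing a random permuted block design stratified by study center". No matching or pairing of subjects across arms is described. Under Secondary Efficacy Endpoints, the same three measures are between-arm comparisons: "Improvement at 12 months will be compared between treatment groups under the following hypotheses".

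**Gate.** The opening paragraph of Secondary Efficacy Endpoints makes secondary testing conditional on both the primary efficacy and the primary safety objectives. Type I Error Control for Secondary Objectives makes it conditional on primary efficacy and adds that the objectives are tested in the listed order; it does not mention safety. Both sections claim an overall Type I error of 5%.

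**The concern.** A signed-rank test asks whether one set of changes, or of paired differences, is centered on zero. With unmatched arms it can only be run on one arm or on the pooled sample, and it then tests change from baseline. Its result depends on the change common to both arms and on how many subjects receive worst ranks. It can reject in either direction when the arms do not differ, and it can miss a difference that exists. This is the analysis in the section aimed at data missing because of death, LVAD, transplant or explant, so the robustness of three secondary results to those events would rest on a test of a different question.

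On the gate, a reader who works only from the Type I error section would go on to test secondary objectives after a missed safety objective; a reader of the endpoint section would not. That choice should be fixed before results are known.

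**Working it through.** **Inputs from the protocol.** Arm size 194: "The treatment group will include 194 subjects randomized to and implanted with" the device, with 194 controls (Study Size and Duration). Safety goal 0.60, assumed rate 0.70, two-sided 95% lower bound, minimum 182 subjects (Primary Safety Endpoint and its sample size section). Efficacy power 0.80. Six-month survival of 84% is a planning figure in the efficacy sample size justification. **Assumed, because the protocol gives no value:** a shared improvement of 0.1 to 0.3 SD, and 0 to 20% of subjects worst-ranked at month 12. The survival figure makes a nonzero share likely.

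**1. The plan's own figures.** Safety sample size: [(1.960 × √(0.6 × 0.4) + 0.842 × √(0.7 × 0.3)) / 0.10]² = 181.1, rounded up to 182, as stated. Overall 5%: with fixed-order testing, primary efficacy certain to pass and all six secondary nulls true, simulated familywise error is 0.050 under the efficacy-only gate and 0.039 under the efficacy-and-safety gate (safety power 0.787). The 5% claim holds under both.

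**2. What signed-rank responds to.** It tests whether the sum of two randomly chosen changes is positive with probability one half. If a share s is placed below all observed values, and observed changes are normal with mean δ in SD units, that probability is (1 − s)² × Φ(√2 δ). At δ = 0.2, Φ(0.283) = 0.611, so it is 0.611 at s = 0, 0.81 × 0.611 = 0.495 at s = 0.10, and 0.64 × 0.611 = 0.391 at s = 0.20. The control arm does not enter.

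**3. Simulation, no arm difference.** 10,000 trials per setting, 194 per arm, normal changes with SD 1, number worst-ranked Binomial(194, s), two-sided 5%, shared shift 0.2 SD:

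| Share worst-ranked | Signed-rank, C-Pulse arm: up | down | Rank-sum, between arms |
|---|---|---|---|
| 0% | 0.771 | 0.000 | 0.051 |
| 5% | 0.240 | 0.001 | 0.049 |
| 10% | 0.022 | 0.032 | 0.049 |
| 15% | 0.001 | 0.287 | 0.048 |
| 20% | 0.000 | 0.752 | 0.053 |

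At shares of 0, 10 and 20%, a shift of 0.1 SD gives 0.278 up, 0.216 down and 0.945 down; a shift of 0.3 SD gives 0.979 up, 0.149 up and 0.427 down. Rank-sum stays between 0.044 and 0.053 in all 15 null settings. Pooling the arms does not help: with a 0.2 SD shared shift and no worst ranks, pooled signed-rank rejects in 97% of trials (2,000 replicates).

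**4. Simulation, real difference.** C-Pulse +0.2 SD, control −0.1 SD, a difference of 0.3 SD. With 10% worst-ranked per arm, signed-rank on the C-Pulse arm rejects in 5.0% of trials and rank-sum in 65.1%. In a 2,000-trial run the pairs are 77% and 83% with none worst-ranked, and 23% and 72% with 5%.

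**5. How often the two gates differ.** The smallest count whose exact (Clopper-Pearson) lower bound exceeds 0.60 is 131 of 194, or 123 of 182. At a true rate of 0.70 the chance of reaching it is 0.798 or 0.787.

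- Efficacy met and safety missed, if independent: 0.80 × (1 − 0.798) = 0.162, or 0.80 × (1 − 0.787) = 0.170.
- With no assumption on dependence, from max(0, 0.80 − power) to min(0.80, 1 − power): 0.002 to 0.202 with 194 implanted, 0.013 to 0.213 with 182.
- If the true safety rate is 0.60, safety is missed in about 98% of trials.

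**The case against.** The strongest reply concerns weight. The sentence states a between-arm purpose and ranks events by time, which fits a rank-sum test, so a competent analyst would probably run the right one. Only a sensitivity analysis is affected. The simulated rates describe a one-arm reading that the protocol never spells out, and they move from 77% up to 75% down with the assumed inputs. The 5%-against-65% contrast is the least favorable of the shares tried; with none worst-ranked it is 77% against 83%. The protocol defers the main secondary methods to the Statistical Analysis Plan, whose text could not be checked. On the gate, both sections use necessary-condition wording, so applying the stricter one satisfies both, and 16-17% is how often the wordings diverge, not an error rate.

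Most of this is right and limits the size of the point. It does not remove it. The missing-data sentence names its own test without deferring to the Statistical Analysis Plan, and nothing else in the protocol corrects it. Multiple imputation is directed at other causes of missing data. The simulations show the consequence of following the text; that signed-rank is the wrong test follows from its definition, whatever shift or share is assumed. Reading the gates together requires noticing both, and the section devoted to Type I error is the one that leaves safety out.

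**Conclusion.** Both parts hold. The named test is wrong for the stated purpose: followed literally, it can reject in roughly three quarters of trials with no arm difference, in a direction set by the worst-ranked share, while rank-sum holds about 5%. Those rates rest on normal changes, a shared 0.2 SD shift and shares of 0 to 20%. It is probably a slip, is confined to a sensitivity analysis, and implies no fault in the main secondary tests.

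The gate wordings differ in substance on the safety condition. Overall Type I error stays at 5% or below under either. At the planning values the prescribed actions diverge in 16-17% of trials under independence. Both points should be corrected; neither threatens the primary analysis.

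**What to change.** 1. In Handling of Missing Data, replace the signed-rank test with the two-sample Wilcoxon rank-sum test comparing C-Pulse with control, keeping the worst ranks ordered by time to outcome.
2. In Type I Error Control for Secondary Objectives, state that secondary objectives are tested in the listed order only if the primary efficacy and primary safety objectives are both met, and make Secondary Efficacy Endpoints agree, including the order.

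The cost is wording only: no added subjects, visits or data. There are two trade-offs. Formal secondary testing is given up whenever safety is missed, in the proportion of trials shown above. A between-arm rank-sum test will also count explants against C-Pulse, because the worst-rank list includes explant, which only implanted subjects can reach; the secondary endpoint definitions do not list it. With an assumed 5% explanted, otherwise equal arms, a 0.2 SD shared shift and 10% or 20% worst-ranked in both arms, rank-sum rejects against C-Pulse in 13-14% of 3,000 simulated trials per setting. That list is the sponsor's choice and is left as written; the sponsor should simply be aware of its effect.

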- *In those intolerant to both ACE-I and ARB, combination therapy with hydralazine and oral nitrate should be considered. Therapeutic equivalence for ACE-I substitutions is allowed within the enrollment stability timelines.*
 - *Aldosterone inhibitor therapy should be added. Eplerenone requires dosage stability for 1 month prior to enrollment.*
 - *Diuretics may be used as necessary to keep the patient euvolemic.*
7. Functional limitation due to heart failure as defined by a 6 Minute Walk test of ≥ 175 ≤ 375 meters, measured within 30 days prior to randomization
 8. At least one hospitalization for decompensated heart failure as defined below, while on heart failure medications, within 12 months prior to randomization or BNP level > 300 or NTproBNP > 1500

Heart failure related hospitalization is defined by the following:

- *signs and symptoms of worsening heart failure; **and***
 - *treatment with intravenous heart failure therapy (including but not limited to diuretic or inotropic therapy) **and***
 - *a minimum of one date change in the hospital*
9. Patient understands the nature of the procedure and on-going device therapy, is willing to comply with associated follow-up evaluations, and provide written informed consent prior to the procedure.

Exclusion Criteria

1. Any evidence, as assessed within 90 days prior to enrollment, of either:
 - a. Ascending aortic calcification on posterior-anterior or lateral chest x-ray
 - b. Calcific ascending aortic disease as detected by non-contrast CT scan
 - c. Ascending aorto-coronary artery bypass grafts, history of aortic dissection, Marfans disease or other connective tissue disorder or repaired aortic coarctation

OR

 - d. Has had an ascending aortic composite graft or root replacement
2. Aorta not conforming to specified dimensional constraints defined by CT scan, most specifically mid ascending aortic outside diameter less than 28 mm or greater than 42 mm

3. Inotrope dependence – inability to wean from inotropic therapy
4. ACC/AHA Stage D heart failure or non-ambulatory NYHA Class IV subject
5. Hypertrophic obstructive cardiomyopathy, restrictive cardiomyopathy, pericardial disease, amyloidosis, active myocarditis, or technically challenging congenital heart disease
6. Clinical signs of severe right heart failure assessed by TAPSE <1.5cm or severe right heart failure precluding LVAD implantation.
7. Reversible cause of heart failure that may be remedied by conventional surgery or other intervention

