Annually Post-Implant	Years 2, 3, 4, and 5 Post Implant (± 30 days of anniversary)

Testing should be conducted at the investigational site. The data collection criteria are summarized in Table 2.

Table 2. Data Collection Summary

Data Collection Requirements							
	Pre-Implant (Baseline)	Implant	Pre-Discharge ²	6 week	3 month	6, 18 month	Annually ¹ Yr 1-5
PATIENT ELIGIBILITY	X						
GENERAL							
Demographic Data	X						
Medical History	X						
General Physical Exam	X	X	X	X	X	X	X
Concurrent Cardiac Meds	X	X	X	X	X	X	X
Weight (Height at enrolment)	X		X	X	X	X	X
Pregnancy test (if applicable)	X						
VITAL PARAMETERS							
Heart rate - (ECG pre-implant)	X		X	X	X	X	X
Blood pressure	X		X	X	X	X	X
Temperature	X		X	X	X	X	X
CARDIOPULMONARY³							
CT aorta	X						Year 1
Chest X-Ray	X						X
ECHO	X				X		X
CPX Testing – Sub Study Only	X						X
QUALITY OF LIFE							
NYHA Classification	X				X	X	X
MLWHF/ KCCQ	X				X	X	X
Six Minute Walk /with Gait Speed	X				X	X	X
HEMATOLOGY							
Hemoglobin	X		X		X	X	X
Hematocrit	X		X		X	X	X
Platelet count	X		X		X	X	X
White cell count	X		X		X	X	X
BIOCHEMISTRY							
Serum sodium	X		X		X	X	X
Serum potassium	X		X		X	X	X
Serum creatinine	X		X		X	X	X
BUN	X		X		X	X	X
BNP or NTProBNP	X					X	X
Serum bilirubin	X		X		X	X	X
Serum ALT	X		X		X	X	X
Serum AST	X		X		X	X	X
Estimated GFR	X						
IMPLANT DETAILS		X					
DEVICE LOG		X			X	X	X
DISCHARGE CHECKLIST			X				

1 Annually post-implant for years 2-5

2 At Discharge - within 36 hours prior and as close to discharge as possible (see Appendix)

3 Imaging may be included to Baseline data collection from within 90days prior to implant.

Summary of Required Testing

Data will be collected and recorded into the web-based database. Paper copies of the database pages (eCRFs) will be made available for the sites.

Device Performance Data – (at all scheduled follow-ups and any clinic visit)

Device performance parameters shall be retrieved following implantation on Day 1, at all follow-up periods. Parameters must be retrieved from the Driver using the Programmer and returned to the sponsor by means of web-based secure data upload.

- Device usage between follow-ups
- Cumulative device usage
- Driver Target Inflation Volume (TIV)
- Driver Inflation Hold Pressure (IHP)

Echocardiographic Testing (Baseline, 3, 12 month and annual follow-up visits)

A transthoracic echocardiography test will be performed at Baseline and at the 3, 12 months and annual follow-up visits.

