Report all associated adverse events. Update the device tracking records with all products. If the device is not returned to Sunshine Heart Inc., justification must be provided in the log.

Subject Withdrawal and Study Exit

A Study Exit record shall be completed if subject is unable to or refuses to continue participation in the study. Notify the Sunshine Heart clinical support team as soon as possible upon learning of a subject withdrawal/study exit.

If the subject fails to comply with follow-up visits, the study center must make repeated attempts to contact the subject. Each attempt to contact the subject must be documented in the subject's records and in the database.

If the subject officially withdraws from the study, the investigator will document the reason for withdrawal and indicate any relationship of the withdrawal to the study or the device on the eCRF.

If a subject withdraws from the study at any time, there will be no penalty or loss of future medical care.

STATISTICAL METHODS AND DATA ANALYSIS

Analysis Population

All randomized subjects will be included in the evaluation of the primary efficacy objective. Subjects will not be allowed to cross-over. All subjects implanted with the C-Pulse System will be included in the evaluation of the primary safety objective. In the event a randomized subject does not receive the implant or does not receive the randomized therapy, the subject will be analyzed according to the randomized assignment for the primary analyses. Additional supporting analyses of the primary efficacy endpoint will be conducted (as treated and per-protocol) which exclude subjects who do not receive the randomized treatment or those with major protocol deviations. The defined analysis cohorts are:

- Intent to treat: All randomized subject irrespective of treatment actually received (primary efficacy analysis)
- As treated: All randomized subjects receiving treatment as randomized
- Per protocol: All randomized subjects without major protocol deviations

Primary Efficacy Endpoint

The primary efficacy endpoint is defined as freedom from worsening heart failure related hospitalization, LVAD implant, heart transplant, and death.

The primary efficacy endpoint includes all occurrences of worsening heart failure events and will be analyzed utilizing a multiple failure time analysis.

Hypotheses

H_0 : HR=1,

H_A : HR \neq 1,

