where HR is the hazard ratio; the ratio of the C-Pulse treatment group worsening heart failure event hazard relative to the Control group worsening heart failure event hazard. This is designed to demonstrate that C-Pulse[®] therapy increases the freedom from worsening heart failure events as compared to Control as evidenced by a HR that is less than 1 and the upper bound of the two-sided 95% confidence interval for the HR excludes 1. All occurrences of worsening heart failure events will be included in the primary endpoint analysis. Details of the analysis methods can be found in the Statistical Analysis Plan.

Primary Efficacy Endpoint Sample Size

Sample size was estimated using SAS v9.2 software under two sided test for a difference in freedom from worsening heart failure. For the purposes of sample size estimation, a time to first event analysis was used to provide a conservative estimate of the required number of events and subjects. The minimum required sample size and total number of worsening heart failure events was calculated under the following assumptions:

- Significance level = 0.05
- Power = 0.80
- Proportion for 6 month freedom from worsening heart failure event in Control group = 0.72
- Underlying treatment effect on the hazard ratio scale: HR = 0.70
- Accrual time of 2.5 years
- Minimum follow-up of 12 months
- 10% Attrition per year
- 1:1 allocation ratio

Under the above assumptions a total of 265 subjects with at least one worsening heart failure events are required to be observed to ensure adequate power which indicates a total of 388 subjects randomized. As the primary analysis will include all worsening heart failure events in a multiple event analysis, the power for the detection of a difference in freedom from worsening heart failure event may be greater than 80%.

Justification for Primary Efficacy Endpoint Sample Size Assumptions

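### The described primary efficacy model names no baseline covariate, although BNP or NT-proBNP and entry route are available at baseline; prespecifying them is a cheap gain in power, not the repair of an error

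*Combined protocol and SAP*

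**What the plan says.** - **Measurement.** Table 2 (Data Collection Summary) has a row for "BNP or NTProBNP", marked at baseline, at months 6 and 18, and annually. Either analyte is accepted.
- **Entry.** Inclusion criterion 8 asks for a hospitalization for decompensated heart failure "within 12 months prior to randomization or BNP level > 300 or NTproBNP > 1500". The peptide is thus an alternative to a prior event of the endpoint's main type. The routes are joined by an or, so a subject may satisfy both.
- **Primary model.** Under Primary Efficacy Endpoint, the endpoint "will be analyzed utilizing a multiple failure time analysis". Under Hypotheses, "All occurrences of worsening heart failure events will be included in the primary endpoint analysis". Neither place names a covariate. The latter adds: "Details of the analysis methods can be found in the Statistical Analysis Plan".
- **Randomization.** The Design section stratifies by study center only.
- **Exploratory covariates.** The section Impact of Covariates on the Potential Treatment Differences plans "covariate adjusted regression analyses for the assessment of interaction with randomization assignment". Besides gender, it says: "Other baseline covariates of interest will include classification based on race/ethnicity, age at implant, INTERMACS profile, NYHA", then etiology, CRT/ICD therapy, angina and the items that close with "arrhythmia, hyperlipidemia and diabetes and the continuous covariates of baseline six-minute walk, KCCQ and MLWHF". No natriuretic peptide and no entry route appear.

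**The concern.** The primary endpoint is made up of worsening heart failure events. The protocol itself treats a raised peptide as an acceptable substitute for a recent heart failure admission, so the peptide is an obvious candidate prognostic covariate. If it predicts the endpoint, a proportional hazards model that includes it has more power than one that does not, at no cost in subjects.

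There are two further gaps. No described analysis asks whether the device effect differs between subjects who entered with a recent hospitalization and those who entered on the peptide alone. And because either analyte may be reported, the raw value cannot be used as one covariate: the protocol's own cut-offs, 300 and 1500, differ five-fold.

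**Working it through.** **1. The plan's own sample size.** Inputs from Primary Efficacy Endpoint Sample Size: two-sided alpha 0.05, power 0.80, HR 0.70, control freedom from event at 6 months 0.72, accrual 2.5 years, minimum follow-up 12 months, attrition 10% per year, 1:1 allocation.

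- Control hazard: −ln(0.72)/0.5 = 0.657 per year. Treatment: 0.70 × 0.657 = 0.460 per year.
- Schoenfeld events: 4 × (1.960 + 0.842)² / (ln 0.70)² = 247.
- With exponential events, uniform accrual and loss hazard −ln(0.9), the average event probability is 0.624. N = 247/0.624 = 396, against the stated 388 (2% apart). The planned N is reproduced.
- 388 × 0.624 = 242 events. Power = Φ(√242/2 × |ln 0.70| − 1.96) = Φ(0.81), about 79%.

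The stated 265 events match 388 × 0.685 = 266, the count without attrition. That is a separate matter.

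**2. Effect of adjustment with the conditional HR held at 0.70.** Simulated first-event trials used 388 subjects and the inputs above. The control hazard was calibrated to 0.72 free at 6 months, and one standard normal covariate stood for log peptide. Cox Wald tests were run at two-sided 0.05. The HR per SD is an assumption. The main run had 3,000 trials per setting.

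| Assumed HR per SD | Power unadjusted | Power adjusted | Gain (points) |
|---|---|---|---|
| 1.0 | 78.9% | 79.0% | 0.1 |
| 1.3 | 77.1% | 80.0% | 2.9 |
| 1.5 | 72.7% | 77.4% | 4.7 |
| 1.8 | 65.1% | 75.9% | 10.8 |

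A separate run of 1,500 trials per setting (Monte Carlo error about 1 point) gave 79/80% at 1.2, 75/78% at 1.4, 69/74% at 1.6 and 60/75% at 2.0. For HR per SD between 1.3 and 1.8, the average unadjusted HR was about 0.71 to 0.73.

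**3. The same question with the unadjusted HR held near 0.70.** The protocol sizes on HR 0.70 and names no covariate, so 0.70 reads naturally as the unadjusted HR. The conditional HR was therefore made stronger until the unadjusted HR was about 0.69 to 0.70. Unadjusted power then stays at about 80% at all three strengths (1.3, 1.5, 1.8), and adjustment adds roughly 2 to 8 points. One set of runs gave 79 to 81% unadjusted and 83 to 89% adjusted. The low unadjusted figures in step 2 therefore come from which HR is fixed, not from a shortfall in the plan.

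**4. Mixing analytes.** Suppose the two assays differ on average by the ratio of the protocol's cut-offs, ln(1500/300) = 1.61. Let a share q of subjects have the second assay, and let s be the SD of log peptide within one assay. Pooling on one log scale without an analyte term keeps s² / (s² + q(1 − q) × 1.61²) of the covariate's explained variance.

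- s = 0.7, q = 0.5: 0.49/(0.49 + 0.25 × 2.59) = 0.43.
- s = 1.3, q = 0.1: 1.69/(1.69 + 0.09 × 2.59) = 0.88.

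The values of s and q are assumptions. Dividing by the analyte's own cut-off and adding an analyte indicator recovers most of the loss.

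**The case against.** The strongest case against has four parts.

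- **The model is deferred.** The protocol sends analysis details to a Statistical Analysis Plan whose text is not in the document reviewed. Silence in the protocol is not a decision against adjustment. This stands: the point concerns the analysis as described, and if that plan already adjusts for the peptide, the primary-model part is settled.
- **The covariate list has another purpose.** It is exploratory, serves interaction testing and is worded as open-ended. Adding the peptide there recovers no power. This also stands, so the power gain rests only on the primary model. The list is still the natural place for the entry-route comparison, and an open list is not prespecification.
- **The unadjusted analysis is sound.** A reader might infer that prognostic information is wasted, that the unadjusted HR is biased toward 1, or that the trial falls short of its power. The documents support none of these. The unadjusted test is valid, the move from 0.70 to 0.71–0.73 is the difference between a conditional and a marginal HR, and step 3 shows planned power intact.
- **The gain is not measured for the actual test.** The simulation uses first events and an error-free covariate with no missing values and a single analyte. The primary analysis counts all events, and the protocol says its power may exceed 80%. This stands as a limit on the figures.

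A reader might also want one analyte required per subject throughout follow-up. The plan contains no analysis of change in peptide, so nothing in it calls for that rule.

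**Conclusion.** The point holds as a recommendation to prespecify. A required baseline measurement that can also decide entry is in no efficacy model or covariate list that the protocol describes, and the same is true of entry route.

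The benefit of adjusting is nil if the peptide is not prognostic, and roughly 2 to 3 points of power at an HR per SD of 1.3, 2 to 6 at 1.5 and 8 to 11 at 1.8. These ranges rest on an assumed prognostic strength, exponential first events and 388 subjects. No separate gain was estimated for entry route. Validity, Type I error and the planned N are not in question.

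**What to change.** Before the interim analysis, which is planned when about 194 subjects have reached 12 months and which carries an efficacy threshold, specify in the primary multiple failure time model:

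- the log of the baseline peptide divided by the protocol's cut-off for that analyte (BNP/300 or NT-proBNP/1500), with the units stated, since criterion 8 gives none;
- an indicator for the analyte;
- entry route, coded as heart failure hospitalization within 12 months, yes or no;
- a simple rule for missing baseline peptide, such as a missing-value indicator.

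Label the result as a conditional HR and report the unadjusted HR beside it. Add entry route and the scaled peptide to the exploratory interaction list. If the sponsor prefers an unadjusted primary analysis, the plan should say so and why.

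The cost is analysis-plan wording, a missing-value rule, and a primary estimate that is conditional rather than marginal. The data come from required baseline and eligibility assessments. The case report forms were not available, so confirm that they record which analyte was measured.
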